9.2 Serious Adverse Events (SAEs)

An SAE is defined as any event that results in any of the following outcomes:

1. Death
2. A life-threatening adverse event;
3. Inpatient hospitalization or prolonging of an existing hospitalization;
4. A persistent or significant incapacity or substantial disruption of the ability to conduct normal life functions; or
5. A congenital anomaly/birth defect.

Important medical events that may not result in death, be life-threatening, or require hospitalization may be considered serious when, based upon appropriate medical judgment, they may jeopardize the subject and may require medical or surgical intervention to prevent one of the outcomes listed above.

Any SAE must be reported by telephone or facsimile within 24 hours of discovery of the event. Investigators should not wait to receive additional information to fully document the event before notifying the Sponsor of an SAE at:

Sites in North America must report to:

Safety Data [contact]

Safety [contact]

Email address (in case of fax failure): [contact]

Sites outside North America must report to the country specific toll-free fax numbers identified below:

Australia: [REDACTED]
Belgium: [REDACTED]
Brazil: [REDACTED]
France: [REDACTED]
Germany: [REDACTED]
Israel: [REDACTED]
Italy: [REDACTED]
Netherlands: [REDACTED]
Spain: [REDACTED]
Sweden: [REDACTED]
United Kingdom: [REDACTED]

Email Address (in case of fax failure): [REDACTED]

The telephone report should be followed by full written summary detailing relevant aspects of the SAE in question using the provided SAE report form. Where applicable, information from relevant hospital case records and autopsy reports should be obtained. The SAE should also be recorded on the AE page of the patient's CRF.

An SAE that occurs after completion of the study but, in the opinion of the Investigator, is related to the study medication, should be reported as described for an SAE. If an AE does not meet the regulatory definition of "serious" but is considered by the Investigator to be related to the study medication and of such clinical concern as to influence the overall assessment of safety, it must be reported as defined for an SAE.

All patients (including discontinued patients) with a SAE must be followed until the event resolves or reaches a new Baseline, but for a minimum of 30 days after the last dose of study drug.

9.3 Suspected Unexpected Serious Adverse Reactions (SUSARs)

The FDA and/or other applicable Regulatory Authorities and all participating Investigators will be notified by a written Investigational New Drug Application (IND) safety report and/or other applicable regulatory report (eg, SUSAR) of any suspected adverse reaction that is both serious and unexpected, no later than 15 calendar days from the "date learned" of the event. In addition, all applicable regulatory bodies will be notified within 7 calendar days of any unexpected fatal or life-threatening suspected adverse reaction.

An adverse reaction is defined as any untoward and unintended response to an investigational medicinal product (IMP) related to any dose administered. This definition also covers medication errors and uses outside what is foreseen in the protocol, including misuse and abuse of the product. The definition also implies a reasonable possibility of a causal relationship between the event and the IMP.

An unexpected adverse reaction is any adverse drug event, which is not listed in the current Investigator's Brochure or is not listed at the specificity or severity that has been observed. For example, (A) a single occurrence of an event that is uncommon and known to be strongly associated with drug exposure (eg, angioedema, hepatic injury, Stevens-Johnson Syndrome); (B) 1 or more occurrences of an event that is not commonly associated with drug exposure, but is otherwise uncommon in the population exposed to the drug (eg, tendon rupture); (C) an aggregate analysis of specific events observed in a clinical trial (such as known consequences of the underlying disease or condition under investigation or other events that commonly occur in the study population independent of drug therapy) that indicates those events occur more frequently in the drug treatment group than in a concurrent or historical control group.

An untoward and unintended response to a non-IMP is by definition not a SUSAR.

9.4 Precautions

9.4.1 Pregnancy

Any patient (or patient's partner) who becomes pregnant during the study should be followed through delivery or termination of the pregnancy. In addition, patients who become pregnant during the study must be discontinued from the study treatment immediately.

In pregnancies that progress to term, any congenital abnormalities/birth defects in the offspring of a patient who received study medication should be reported as an SAE. The outcome of the pregnancy and the presence or absence of a congenital abnormality will be documented by completion of a Pregnancy Questionnaire and a Pregnancy Outcome Form in accordance with GCP and ICH guidelines and the Sponsor's SOPs.

Female patients should also notify the Investigator if they become pregnant within 30 days after last dose of study medication. Male patients should notify the Investigator if a female partner becomes pregnant within 30 days after last dose of study medication. The Sponsor must be notified of all pregnancies reported to the Investigator (see [Section 9.2](#) for contact information).

10. Statistical Methodology

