6.1 Inclusion Criteria

Patients must meet all of the following criteria to be considered eligible to participate in the study:

1. Ongoing participation in a Phase 2 (eg, LX1606.1-202-CS, LX1606.1-203-CS) or Phase 3 (eg, LX1606.1-301-CS, LX1606.1-303-CS) study
2. Patients of childbearing potential must agree to use an adequate method of contraception (defined as having a failure rate of <1% per year) during the study and for 12 weeks after the Follow-up visit. Adequate methods of contraception for patients or partner include condoms with spermicide gel, diaphragm with spermicide gel, coil (intrauterine device), surgical sterilization, vasectomy, oral contraceptive pill, depot progesterone injections, progesterone implant, and abstinence during the study and for 12 weeks after the Follow-up Visit.
 - a. Childbearing potential is defined as those who have not undergone surgical sterilization, or those who are not considered postmenopausal. Postmenopause is defined as absence of menstruation for at least 2 years. If necessary, follicle-stimulating hormone (FSH) results >50 IU/L at Screening are confirmatory in the absence of a clear postmenopausal history.
3. Ability and willingness to provide written informed consent prior to participation in any study-related procedure.

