6.3 Criteria for Stopping Treatment/Study Withdrawal

A patient may also be discontinued from the study for the following medical or administrative reasons:

- Withdrawal of consent by the patient or legal guardian
- Noncompliance, including refusal of the study medication and/or failure to adhere to the study requirements as in the study protocol
- Investigator decides that, in the interest of the patient, it is not medically acceptable to continue participation in the study
- The Sponsor terminates the study ([Section 6.4](#))
- Pregnancy ([Section 9.4.1](#))

Note: If a patient voluntarily withdraws or is discontinued from study treatment before completing the entire duration of the Treatment Period, they should be encouraged to continue clinic visits according to the study schedule.

Patients who discontinue study treatment, and who are not willing to continue clinic visits (eg, withdrawal of consent) should be encouraged to complete End-of-Study (EOS) assessments as identified in [Appendix A](#) – Schedule of Events and agree to report any SAEs (Section 9.2) that occur within 30 days following the last dose of telotristat etiprate.

The date the patient discontinues study treatment, the primary reason for study treatment discontinuation, study termination, and/or termination of participation (eg, withdrawal of consent), will be captured within the Case Report Form (CRF).

When patients withdraw consent from study participation, it must be recorded on the CRF whether the withdrawal of consent applies to specific aspects of the study such as discontinuation of study treatment, participation in study visits, contact by study personnel, or

access to information about potential SAEs. If specific consent has not been withdrawn, study personnel should contact the patient (or a previously approved designee such as a caregiver, partner, or family member) at the scheduled Follow-up visit to inquire about health status.

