¹Eligibility will be determined at last visit of the original protocol; Day 1 will replace the next scheduled visit in the original protocol schedule. Visits should coincide with LAR injections for those patients receiving SSA therapy. ²Females of child-bearing potential only. ³Brief physical examination only (symptom-oriented, including weight). ⁴Visit to be performed for subjects who withdraw early and will not return for a 2 week follow-up visit; In all other cases the EOS visit should be performed followed by the follow-up visit 2 weeks postdose. ⁵To be performed only if evaluation at Week 48/EOS is abnormal.

14. Appendix B – Amount of Blood to be Collected from Each Patient

Assessment		Sample volume (mL)	Number of samples*	Estimated total volume (mL)
Safety	Hematology	2	6	12
	Blood chemistry	6	6	36
Other	CgA	2	2	4
	Serum Pregnancy	2	1	2
Pharmacodynamic	Plasma 5-HIAA	4	6	24
Total				78
*Maximum number of samples is indicated				

15. Appendix C – EORTC QLQ-C30

EORTC QLQ-C30 (version 3)

We are interested in some things about you and your health. Please answer all of the questions yourself by circling the number that best applies to you. There are no "right" or "wrong" answers. The information that you provide will remain strictly confidential.

Please fill in your initials:
 Your birthdate (Day, Month, Year):
 Today's date (Day, Month, Year): 31

	Not at All	A Little	Quite a Bit	Very Much
1. Do you have any trouble doing strenuous activities, like carrying a heavy shopping bag or a suitcase?	1	2	3	4
2. Do you have any trouble taking a long walk?	1	2	3	4
3. Do you have any trouble taking a short walk outside of the house?	1	2	3	4
4. Do you need to stay in bed or a chair during the day?	1	2	3	4
5. Do you need help with eating, dressing, washing yourself or using the toilet?	1	2	3	4
During the past week:				
6. Were you limited in doing either your work or other daily activities?	1	2	3	4
7. Were you limited in pursuing your hobbies or other leisure time activities?	1	2	3	4
8. Were you short of breath?	1	2	3	4
9. Have you had pain?	1	2	3	4
10. Did you need to rest?	1	2	3	4
11. Have you had trouble sleeping?	1	2	3	4
12. Have you felt weak?	1	2	3	4
13. Have you lacked appetite?	1	2	3	4
14. Have you felt nauseated?	1	2	3	4
15. Have you vomited?	1	2	3	4
16. Have you been constipated?	1	2	3	4

Please go on to the next page.

During the past week:

	Not at All	A Little	Quite a Bit	Very Much
17. Have you had diarrhea?	1	2	3	4
18. Were you tired?	1	2	3	4

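### Contraception is required until about day 98 after the last dose, but patients are asked to report only pregnancies that begin by day 30; the reporting window should run as long as the contraception rule

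*Protocol*

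**What the plan says.** The rules below are those of Amendment 1 (31 January 2014). The same pairing of Sections 6.1 and 9.4.1 appears in the original version and in the Amendment 1 version that carries the French appendices.

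- **Contraception.** Section 6.1, criterion 2, obliges patients of childbearing potential to use an adequate method "during the study and for 12 weeks after the Follow-up visit".
- **Timing of the Follow-up visit.** Section 5.1 sets a 14-day off-drug Follow-up Period for all patients. Appendix A, footnote 4, lets the visit be done for early withdrawals who will not come back two weeks later. Otherwise: "In all other cases the EOS visit should be performed followed by the follow-up visit 2 weeks postdose". The schedule allows ±5 days.
- **Notification.** Section 9.4.1: "Female patients should also notify the Investigator if they become pregnant within 30 days after last dose of study medication". Male patients have the same 30-day limit for a partner's pregnancy.
- **Outcome follow-up.** Section 9.4.1 has any patient or partner "who becomes pregnant during the study should be followed through delivery or termination of the pregnancy".
- **Onward reporting.** "The Sponsor must be notified of all pregnancies reported to the Investigator", with no time limit.

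The later text at the front of the document repeats the 30-day wording in Section 9.4.1. Its Section 6.1 is not shown.

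**The concern.** The 30 days limits when the pregnancy begins, not when it must be reported. A patient who conceives on day 60 after the last dose, while still bound by the contraception rule, is under no stated duty to tell the site.

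Nor would the schedule find it. On the standard path the last planned pregnancy test and adverse-event check is the Follow-up visit. After that the Sponsor depends on the patient coming forward, and the protocol asks for that only up to day 30. A contraceptive failure in this period is the event the rule in Section 6.1 is meant to prevent. In a study whose primary objective is long-term safety, such a pregnancy and its outcome could go unrecorded.

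The documents give no half-life or reproductive data, so no specific drug risk is claimed for days 31 to 98.

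**Working it through.** This is date arithmetic, with day 0 as the last dose. The protocol prints no day count for the end of contraception, so there is no figure of its own to reproduce.

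**Inputs**
- Follow-up visit: day 14, or days 9 to 19 with the ±5-day tolerance (Section 5.1; Appendix A and footnote 4).
- Contraception after that visit: 12 × 7 = 84 days (Section 6.1, criterion 2).
- Notification limit: day 30 (Section 9.4.1).

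**Formulas**
- End of contraception = Follow-up visit day + 84.
- Uncovered days = end of contraception − 30.
- Share of the post-dose contraception period = uncovered days ÷ end of contraception.

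| Case | Follow-up visit | End of contraception | Uncovered days | Share |
|---|---|---|---|---|
| Standard, earliest | 9 | 9 + 84 = 93 | 93 − 30 = 63 | 63/93 = 68% |
| Standard, nominal | 14 | 14 + 84 = 98 | 98 − 30 = 68 | 68/98 = 69% |
| Standard, latest | 19 | 19 + 84 = 103 | 103 − 30 = 73 | 73/103 = 71% |
| Early withdrawal, visit at last dose (assumed) | 0 | 0 + 84 = 84 | 84 − 30 = 54 | 54/84 = 64% |

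A Follow-up visit on days 0 to 9 gives gaps of 54 to 63 days, so the range runs continuously from 54 to 73.

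**After the last scheduled pregnancy test.** Of the 84 contraception days that follow the Follow-up visit, notification covers 30 − 14 = 16 on the standard path (11 to 21 with the tolerance). That leaves 68/84 = 81% uncovered (63/84 = 75% to 73/84 = 87%). In the early-withdrawal case it leaves 54/84 = 64%.

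**Expected events.** The number of patients using contraception is not given. If all 100 expected patients did so, at the criterion's ceiling failure rate of 1% per year, the 68-day gap would produce 100 × 0.01 × 68/365.25 = 0.19 pregnancies. The true number of users is probably lower, which would reduce this figure.

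**Do other clauses close the gap?**
- Follow-up through delivery is tied to pregnancies during the study.
- Birth defects are SAEs without a time limit (Section 9.4.1), and drug-related SAEs after completion are reportable (Section 9.2).
- The Sponsor must be told of any pregnancy the Investigator hears of.

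The last two bullets help only once the site knows of the pregnancy, and no clause asks the patient to tell the site after day 30. Patients who stop drug early but keep attending visits remain covered while they attend.

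**The case against.** The best defence is that the two windows do different jobs. Twelve weeks of contraception is a cautious preventive margin. The 30-day notification limit follows the protocol's safety-surveillance convention, which also governs AE follow-up (Section 9.1), minimum SAE follow-up (Section 9.2), on-study deaths (Section 10.4.2.1) and the SAEs that withdrawn patients agree to report, namely those "that occur within 30 days following the last dose of telotristat etiprate" (Section 6.3). Nothing says the windows must match, and without pharmacokinetic or reproductive data nobody can show that 30 days is too short. The birth-defect and onward-reporting clauses are untimed, as is the sentence on the pregnancy outcome forms. Sponsor SOPs or the consent form, neither shown, may ask for more. The percentages are shares of calendar days, not of risk, and the 54-day case sits awkwardly with the 14-day Follow-up Period that Section 5.1 requires of everyone.

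Much of this stands. There is no contradiction, the expected number of events is very small, and the day-0 case is only an assumed lower bound. A longer window would still rely on passive self-report.

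What does not stand is the inference that the 30-day rule is adequate. The AE and SAE limits do not address a contraceptive failure within the protocol's own prevention period, and the untimed clauses operate only after the site has been told.

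**Conclusion.** The point holds as a low-severity design improvement. Amendment 1 leaves about 68 days (63 to 73) of required contraception in which a new pregnancy need not be reported. The lower bound is 54 days if an early withdrawal has the Follow-up visit on the day of the last dose. No endpoint, analysis or sample size is affected.

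Two limits apply:

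- **Later text.** The mismatch can be verified only in the versions shown with both sections. Amendment 2's list of changes names criterion 2.a as the only inclusion criterion altered, so the 12-week rule probably carried forward, but this is inference. The April 2015 Netherlands addendum still works from the Amendment 1 text.
- **Male patients.** It is unclear whether criterion 2 binds them. Criterion 2.a reads: "Childbearing potential is defined as those who have not undergone surgical sterilization, or those who are not considered postmenopausal", which points to women through its reference to menopause. Yet the criterion also says: "Adequate methods of contraception for patients or partner include condoms with spermicide gel". The partner part of the point is therefore conditional.

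**What to change.** In Section 9.4.1, replace the 30-day limit for female patients so that notification and outcome follow-up cover any pregnancy beginning up to 12 weeks after the Follow-up visit. If criterion 2 is meant to bind male patients, state that in Section 6.1 and apply the same window to their partners. Align the consent form if it states 30 days.

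The cost is one or two sentences in the protocol and possibly one in the consent form. No visits, tests or analyses are added; patients and sites carry a longer passive reporting duty. The Netherlands addendum announces a further amendment, which would be a convenient place for the change.

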10.1 Determination of Sample Size

No formal sample size calculation was made. The number of patients expected to participate in this study was calculated from estimated enrollment rates from other carcinoid cancer trials employed in the LX1606 clinical program.

10.2 Analysis Populations

Per protocol: A Per Protocol population will consist of those patients that receive study treatment and have no major protocol violation that would interfere with the collection or interpretation of the efficacy data. The primary analyses of efficacy will be based on the safety population; the per-protocol population will be used in a supplemental manner.

Safety: The safety population consists of all patients receiving any fraction of a dose of study drug during this study.

10.3 Study Endpoints

10.3.1 Efficacy Endpoints

The primary efficacy endpoint is to evaluate the long-term safety and tolerability of orally administered telotristat etiprate.

Secondary efficacy endpoint is to evaluate changes in patients' QOL over multiple years of therapy.

10.3.2 Safety Endpoints

Safety endpoints are as follows:

- Incidence of TEAEs, suspected adverse reaction, AEs leading to discontinuation from the study, SAEs, and deaths
- Actual and change from Baseline in clinical laboratory results
- Actual and change from Baseline in vital signs results
- Actual and change from Baseline in physical examinations
- Actual and change from Baseline in ECG findings

10.4 Statistical Methods

Descriptive analysis methods will be used to summarize the data. Continuous variables will be summarized by the N, mean, standard deviation, median, minimum, and maximum values.

Categorical variables will be summarized as counts and related percentages. Data tabulations will be categorized by the treatment received on Day 1 of this study and combined across all treated patients. All data will be listed.

Primary analyses of the data will be based on the Safety population which includes all patients treated with any fraction of study drug during this study. Supportive analyses of the efficacy data will be made on a Per Protocol population. This dataset will include the Safety population, but limited to those patients that have at least one assessment post Day 1 and do not have any protocol violations that would interfere with collection or interpretation of the data. The Per Protocol analysis will be applied to the QOL measures, subjective global assessment, and plasma 5-HIAA values.

Data will be summarized per study visit as the actual (raw) outcomes and change from Baseline scores, where applicable. Day 1 of this study will serve as the Baseline assessment.

10.4.1 Efficacy Analyses

All efficacy and PD variables will be summarized descriptively and listed.

Statistical tests and estimates of within patient effects for these measures will be derived from application of a mixed linear model with repeated measures. The model will be generalized to handle missing data and specific to the measurement properties of the dependent variable. There is no plan to impute data for missing observations for any variable. Non-parametric methods will be used to supplement the tests and estimates from the mixed linear model.

Exploratory analyses of treatment group differences may be performed by use of propensity score models. The treatments groups will correspond to how patients were dosed on Day 1 of this study.

10.4.2 Safety Analyses

Statistical analysis of the safety data will involve examination of the descriptive statistics and individual patient listings for any effects of study treatment on clinical tolerability and safety. Reporting of these data will be based on the Safety population. Summaries will be prepared by treatment group (corresponding to the LX1606 dose given on Day 1), pooled across all patients, and as needed, by study visit. All safety data will be listed.

Treatment-emergent adverse event summaries will include the overall incidence (by system organ class and preferred term), events by maximum intensity, event by relationship to study treatment, events leading to discontinuation of study drug, and serious adverse events.

Vital signs, ECG, and laboratory parameters (hematology, chemistry, and urinalysis) will be summarized descriptively at each time point. Actual and change from Baseline data will be

calculated and summarized. In addition, shift table analysis will be applied to the laboratory data and summarized.

10.4.2.1 Adverse Events

All AEs will be coded and listed by body system and preferred term based on the Medical Dictionary for Regulatory Activities (MedDRA). Summaries using descriptive statistics will be provided for treatment-emergent AEs, drug-related AEs and AEs by intensity. Treatment-emergent AEs are those events not present at Baseline, but occurring after the start of study drug, or if existing at Baseline, increasing in intensity after initiation study drug. Summaries made by intensity will select the event with the highest intensity when multiple occurrences of the same event are reported for the same patient. In a similar manner, summaries prepared by drug relationship will select the event with the greatest degree of relationship when a study reports multiple occurrences of the same event. On-study deaths will be reported for deaths occurring during the active phase of the treatment period and 30 days after stopping study drug. Also, deaths occurring outside the 30-day window, but secondary to an AE reported within the 30-day post treatment period, will be reported as well.

Listings will be provided for deaths, SAEs, and discontinuations due to AEs. Additional summaries or listings of AEs may also be provided.

